7.5 Study Visits

Subject visits will follow a standard visit schedule:

	Eligibility Confirmation & Enrollment	48 +/- 24 Hours	Day 30 +/- 7	Day 90 +/- 7
Screening	X			
Informed Consent	X			
Eligibility [Inclusion & Exclusion]	X			
Blood Pressure	X			X
mRS	X			X
NIHSS	X			X
Outcomes	X		X	X
AE Screening		X	X	X

8. STATISTICAL ANALYSIS

Demographics and past medical history variables will be summarized for all subjects using means or medians as appropriate for continuous variables and proportions for categorical variables. We will compare the two study arms using Student's t-test or Wilcoxon rank sum as appropriate for continuous variables and χ^2 test for categorical variables.

The primary outcome measure is adherence with blood pressure monitoring during the study period. Adherence will be defined by dividing the number of successfully completed BP measurements (numerator) by the expected number of BP measurements (denominator). The expected number of BP measurements is the number of days that the subject is in the study multiplied by 2. Most subjects will be enrolled in the study for 90 days and will therefore be expected to check their BP 180 times. Adherence in this case is the number of completed BP measurements divided by 180. The 90-day follow-up visit has a window of +/- 7 days, so for subjects that complete the study protocol the denominator will be adjusted accordingly. Subjects whom withdrawal from the study and/or stop monitoring their BP before the 90-day follow-up visit will remain in the analysis. These subjects will be considered non-adherent for all BP measurements after they cease taking measurements and the denominator will be set at 180. As an example, if a subject checks their BP 60 times in the first 75 days of the study and then ceases all BP measurements, adherence will be calculated as $60/180=33.3\%$. After adherence has been calculated for all subjects we will evaluate the distribution of adherence for normality and compare adherence between the two study arms using Student's t-test or Wilcoxon rank sum as appropriate. A sample size of 90 will give us 80% power to detect a 30% difference between groups with $\alpha=0.05$.

Additional analysis will compare the change in blood pressure between the two groups. The mean systolic and diastolic blood pressure in the first 7 days of the 90 day study period and the last 7 days of the 90 day study period will be calculated for each subject. The average change in blood pressure will be compared between study arms using Student's t-test or Wilcoxon rank sum as appropriate. We will also compare the proportion of subjects with an average blood pressure <140/90 mm Hg in the final week of the study between groups using χ^2 . Subjects who drop out of the study or cease monitoring their BP prior to day 90 will be included in these analyses if they have a minimum of 14 days of monitoring. For these subjects, we will utilize BP readings from the last 7 days of monitoring. The use of earlier readings carried forward should be conservative and bias the results toward the null. Exclusion of subjects with less than 14 days of monitoring may truncate our sample and introduce bias, so we will conduct a sensitivity analysis in which we impute a change in BP for subjects with less than 14 days of monitoring of zero.

We will compare secondary outcomes across study arms including number of calls to the study team, number of physician visits, number of emergency department visits, number of changes in antihypertensive medications, and the patient perception of: study protocol, utility of blood pressure monitoring, and blood pressure control. We will also determine the relationship between adherence to blood pressure monitoring and change in blood pressure during the study period. For this analysis, we will first determine the average adherence in the study population. We will compare the change in blood pressure in those with above average adherence to those with below average adherence. This will be done in the full study population and then stratified by study arm. In an exploratory analysis multivariable regression will be utilized to determine which factors were associated with a high level of adherence to the study protocol, defined as adherence above the study median. We will investigate the following variables in a univariate analysis: age, sex, race, ethnicity, income, social support in the home, employment status, MMSE score, NIHSS, and modified Rankin Scale. Variables in the univariate analysis with $p < 0.10$ will be incorporated into a multivariable logistic regression model. We will test for an interaction between the social incentive and the variables in the multivariable model.

9. Data Handling and Record Keeping

9.1 Confidentiality.

- Paper-based records will be kept in a secure location and only be accessible to personnel involved in the study.
- Computer-based files will only be made available to personnel involved in the study through the use of access privileges and passwords.
- Prior to access to any study-related information, personnel will be required to sign statements agreeing to protect the security and confidentiality of identifiable information.
- Whenever feasible, identifiers will be removed from study-related information.

- A Certificate of Confidentiality will be obtained, because the research could place the subject at risk of criminal or civil liability or cause damage to the subject's financial standing, employability, or liability.
- A waiver of documentation of consent is being requested, because the only link between the subject and the study would be the consent document and the primary risk is a breach of confidentiality. (This is not an option for FDA-regulated research.)
- Precautions are in place to ensure the data is secure by using passwords and encryption, because the research involves web-based surveys.
- Audio and/or video recordings will be transcribed and then destroyed to eliminate audible identification of subjects.
- Other (*specify*): _____

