4.2 Accrual

The study will enroll a total of 90 patients at the Hospital of the University of Pennsylvania (HUP).

The study will be powered on the primary objective of the study, which is to compare adherence with twice daily blood pressure monitoring in subjects with and without a social incentive. Based on data in other study populations, we expect a 50% adherence rate in subjects without a social incentive.

A sample size of 90 subjects will provide 80% power to detect a 30% difference in adherence between groups. This calculation is based on a two-sample comparison of means, with $\alpha=0.05$.

Patients will be identified from the inpatient stroke service and the outpatient neurology clinic at the Hospital of the University of Pennsylvania. It is expected that we will complete enrollment in 15 months and the study will be completed in 2 years.

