5.2 Design

This is a single center randomized trial designed to assess the effectiveness of a social intervention to improve adherence with home blood pressure monitoring. Computer-based block randomization (block size=4) will be used to maintain relatively equal numbers of subjects in both arms of the study. This study will provide important preliminary data for future studies, which will use behavioral incentives to improve adherence to home blood pressure monitoring and titration of antihypertensive therapy.

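### The primary adherence comparison is valid but uses none of the baseline factors already collected, and the planned baseline significance tests add nothing; a small pre-specified adjusted model would be a cheap improvement.

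*Combined protocol and SAP*

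**What the plan says.** Four places in the combined protocol and SAP bear on this.

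- **Primary comparison (Section 8).** Once each subject's adherence has been calculated and its distribution examined, the plan will "compare adherence between the two study arms using" a t-test or Wilcoxon test. No covariate is named, and no adjusted analysis of the arm difference appears elsewhere.
- **Baseline comparison (Section 8).** Directly after describing how demographics and past medical history will be summarized, the plan says "We will compare the two study arms using" a t-test, Wilcoxon or chi-square test. The natural reading is a set of between-arm tests on baseline variables.
- **Candidate predictors (Sections 1.2, 7.1 and 8).** A secondary objective asks which individual factors go with adherence. Section 8 lists ten: "We will investigate the following variables in a univariate analysis: age, sex, race, ethnicity, income, social support in the home, employment status, MMSE score", followed by NIHSS and modified Rankin Scale. Section 7.1 records age, whether the subject lives alone, and MMSE at enrollment.
- **Randomization (Section 5.2).** "Computer-based block randomization (block size=4) will be used to maintain relatively equal numbers of subjects in both arms". No stratification factor is named.

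**The concern.** Neither the design nor the primary analysis makes use of patient factors that may be related to adherence. Randomization balances such factors on average. In a single trial of 90, though, one of them can differ between arms by chance, and a two-group test leaves the resulting shift in the estimate. The planned baseline tests could draw attention to such a difference but would do nothing about it, and the plan gives no rule for acting on a flag.

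The exploratory model in Section 8 does not fill the gap. It splits adherence at the median, selects variables at p < 0.10, and brings in arm through interaction tests. It gives no adjusted difference in adherence between arms.

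At stake are some precision and some robustness to chance imbalance, in a trial meant to inform later studies.

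**Working it through.** **Inputs from the documents.** N = 90, taken as 45 per arm under 1:1 allocation (Section 7.1). Section 4.2 states: "A sample size of 90 subjects will provide 80% power to detect a 30% difference in adherence between groups". On method it says: "This calculation is based on a two-sample comparison of means". Control adherence is 50% and alpha is 0.05, taken here as two-sided. No SD is given.

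**The plan's own figure.** Without an SD, N = 90 cannot be reproduced directly. Solving for the SD that gives 80% power with 45 per arm, SD = difference / [(1.960 + 0.842) × √(2/45)]:

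- 30% read as 30 points: 0.30 / (2.802 × 0.2108) = 0.508.
- 30% read as relative (50% to 65%): 0.15 / (2.802 × 0.2108) = 0.254.

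The power gain below is the same for either SD.

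**Effect of adjustment.** If covariates explain a share R² of the variance, the residual SD is SD × √(1 − R²). Power is then Φ(2.802/√(1 − R²) − 1.960). The R² values are assumed, and the few degrees of freedom spent are ignored.

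| R² (assumed) | Power at N = 90 | N for 80% power | Detectable difference (30-point reading) |
|---|---|---|---|
| 0 | 80% | 90 | 30.0 points |
| 0.05 | 82% | 86 | 29.2 points |
| 0.10 | 84% | 82 | 28.5 points |
| 0.20 | 88% | 72 | 26.8 points |

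**Is the unadjusted test valid?** In 20,000 simulated trials of 45 per arm with one prognostic covariate, its type I error was 4.9-5.0% for R² of 0.1, 0.2 and 0.3. In the roughly 5% of trials where that covariate differed between arms at p < 0.05, the false-positive rate was about 10%, 15% and 21% respectively. A baseline test would pick out those trials and change nothing in them.

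**Size of a chance imbalance (illustration; prevalence and effect assumed).** For a factor present in 30% of subjects, the SD of the arm difference is √(2 × 0.3 × 0.7/45) = 0.097, or 9.7 points. A difference of 15 points or more has probability 12% by normal approximation and 17% by an exact hypergeometric count. If the factor shifts adherence by 20 points, the estimate moves 0.15 × 20 = 3 points. The standard error of the arm difference is SD × √(2/45) = 5.4 points (SD 0.254) or 10.7 points (SD 0.508). The shift is therefore 3/5.4 = 0.56 or 3/10.7 = 0.28 of a standard error.

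**False flags from baseline tests (independence assumed).** Section 7.1 lists 4 demographic items and 10 medical-history items. Expected flags: 14 × 0.05 = 0.7. Chance of at least one: 1 − 0.95^14 = 51%. If all enrollment items were tested, about 33 by count, these become 33 × 0.05 = 1.65 and 1 − 0.95^33 = 82%.

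**The case against.** The strongest reply is that nothing is broken. An unadjusted comparison in a 1:1 trial with no stratification factor keeps its 5% level, and its standard error already allows for chance imbalance over repeated randomizations. The illustrative 3-point shift is well under one standard error. This is a pilot, and adjustment is an option for precision. All of that stands.

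Some stronger readings might be inferred, and the documents do not support them:

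- That the plan expects these factors to predict adherence. Section 1.2 asks an open question, and Section 8 screens candidates in an analysis it calls exploratory.
- That the baseline tests are offered in place of adjustment, or will steer the choice of covariates. No text links them to the primary test.
- That the tests are bound to flag something. For 14 items it is close to an even chance.
- That randomization balances only arm size. Blocking controls arm size, while randomization balances every factor in expectation.

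Two objections to the remedy also carry weight. First, any short list of covariates is a judgment. MMSE has a restricted range because Section 4.4 excludes scores of 20 or below. Living alone may matter less because Section 4.3 requires every subject to have an identifiable support person. Second, a linear model alone would drop the rank-based option for a bounded and possibly skewed outcome. That is a reason to keep the unadjusted test in the report. It does not argue against adding an adjusted one.

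**Conclusion.** The point holds as an inexpensive improvement. A reader might conclude that the primary analysis is biased or invalid for want of covariates. It is not: its type I error is about 5%. What is lost is some precision and some protection against a chance imbalance. If covariates explain 5-20% of the variance, the gain is 2 to 8 percentage points of power at N = 90. That range is assumed, because the documents give nothing from which to estimate it, and the true gain could be negligible.

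The baseline significance tests have no useful role under proper randomization. Their chance of at least one false flag is about 51% for 14 independent items and higher if more are tested. This rests on reading the Section 8 sentence as applying to baseline variables, which its position supports.

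**What to change.** Before arm-level data are seen, revise Section 8 as follows.

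1. Pre-specify a linear model of adherence on arm plus a few named baseline covariates, for example age, lives alone (yes/no) and MMSE. Report the adjusted arm difference with robust standard errors and a 95% confidence interval.
2. Report the planned unadjusted t-test or Wilcoxon test beside it, which keeps a rank-based check. State in advance which of the two carries the primary conclusion.
3. Present baseline characteristics by arm as summaries without p-values.

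The cost is Section 8 wording and, with the three example covariates, three degrees of freedom. No new data are needed. The downside is little or no gain if the chosen covariates turn out to be weakly related to adherence.

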4.3 Inclusion Criteria

1. Adult, age ≥ 18 years
2. History of ischemic stroke, intraparenchymal hemorrhage, or high risk TIA (defined by ABCD2 ≥ 4) with the past 5 years prior to enrollment
3. Hypertensive at time of screening, defined by SBP >140 mm Hg or DBP >90 mm Hg
4. Enrollment must occur within 30 days of study screening
5. Must own a smart phone capable of interacting with the connected blood pressure cuff (Apple iPhone 3GS or higher; Android 4.0 or higher with Bluetooth connectivity)
6. Must be able to identify at least one adult (≥ 18) with internet access and/or a smart phone with text messaging capability who could serve as a social support person.
7. Willingness and ability to sign informed consent by patient

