3. National Institute of Health Stroke Scale (NIHSS). The NIHSS is a brief, structured neurologic examination, designed to assess deficits from stroke (figure 2). Study personnel will be trained and certified in the use of the NIHSS.

4. Heart Rate and blood pressure – Heart rate and blood pressure will be measured at least 30 minutes after exercise. The patient will have been sitting for at least 5 minutes before blood pressure is checked. The patient will be asked to sit in a chair with their back straight and supported and their feet flat on the floor. The arm will be supported on a flat surface at approximately the level of the heart. Blood pressure and heart rate will be assessed in the non-dominant arm using an

NIH Stroke Scale	
1a. LOC 0 alert 1 drowsy 2 stuporous 3 coma	6. Motor Leg a. Left Leg 0 no drift 1 drift 2 cannot resist gravity 3 no effort against gravity 4 no movement
1b. LOC ?'s 0 both correct	
Figure 2. NIH Stroke Scale	
1c. LOC Commands 0 both correct 1 one correct 2 incorrect	7. High Leg 0 no drift 1 drift 2 cannot resist gravity 3 no effort against gravity 4 no movement z amputation/joint fusion
2. Best Gaze 0 normal 1 partial gaze palsy 2 forced deviation	8. Limb Ataxia 0 absent 1 present in one limb 2 present in two limbs
3. Visual Fields 0 no visual loss 1 partial hemianopsia 2 complete hemianopsia 3 bilateral hemianopsia	9. Sensation 0 normal 1 partial loss 2 severe loss
4. Facial Palsy 0 normal 1 minor 2 partial central 3 complete	10. Best Language 0 no aphasia 1 mild-mod aphasia 2 severe aphasia 3 mute
5. Motor Arm a. Left Arm 0 no drift 1 drift 2 cannot resist gravity 3 no effort against gravity 4 no movement z amputation/joint fusion	11. Dysarthria 0 none 1 mild-mod 2 severe/mute z intubated
b. Left Arm 0 no drift 1 drift 2 cannot resist gravity 3 no effort against gravity 4 no movement z amputation/joint fusion	11. Extinction 0 no neglect 1 partial neglect 2 complete neglect
Total Score	

automated sphygmomanometer. This will be repeated for a total of three measurements, which will be averaged to determine the baseline blood pressure.

Education

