Patients will be randomly assigned (1:1) to either receive a social incentive or not. The social incentive will require the subject to identify a social supporter. This individual can be a family member, friend, or other community member selected by the subject. The social supporter will need to assent to the study and register on the Way to Health platform. The social supporter will receive education on the importance of hypertension, how to measure blood pressure, and how to operate the Withings monitor. If the social supporter is not present at the time of subject enrollment, they may assent to the study via telephone and/or by registering online at the Way to Health platform. In this scenario they will receive education via telephone and/or online.

The social supporter will choose whether they prefer to receive study communications via text message or email. The social supporter will receive a text or email message alert at 11:00am if the subject has not completed their morning BP reading and at 9:00pm if the subject has not completed their evening BP reading. The social supporter will also receive feedback on the subject's BP control from the Way to Health platform on a weekly basis. This message will summarize the subject's adherence to home monitoring in the preceding 7 days. It will also contain the subject's mean BP over the preceding 7 days and note whether the subject's BP is above or below a goal of <140/90 mm Hg. The expectation is that the social support person will provide further feedback to the subject in order to improve both adherence and BP control.

Non-adherence

BP readings will be automatically uploaded from the subject's smartphone to the Way to Health platform. If the subject goes 7 days without a single BP measurement, Way to Health will alert study personnel. Study personnel will contact the subject by phone to remind them to check their BP and troubleshoot any potential technical

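### Neither between-arm blood pressure comparison adjusts for starting blood pressure; both are valid, but each gives up some precision at no saving

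*Combined protocol and SAP*

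**What the plan says.** Section 8 (Statistical Analysis) builds change in BP from home readings: "The mean systolic and diastolic blood pressure in the first 7 days of the 90 day study period and the last 7 days" are averaged for each subject. It then states: "The average change in blood pressure will be compared between study arms using Student's t-test or Wilcoxon rank sum as appropriate". A second analysis follows: "We will also compare the proportion of subjects with an average blood pressure <140/90 mm Hg in the final week of the study", by chi-square. Subjects who stop early are "included in these analyses if they have a minimum of 14 days of monitoring", using their last 7 monitored days. A sensitivity analysis gives those with less monitoring a change of zero.

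Neither comparison has a covariate. The only regression in Section 8 models high adherence, not BP.

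Section 4.3 sets entry on BP as "Hypertensive at time of screening, defined by SBP >140 mm Hg or DBP >90 mm Hg" and adds "Enrollment must occur within 30 days of study screening". Nothing requires BP to be above goal at enrollment or in the first home week. Section 7.1 also takes three clinic readings at enrollment, "which will be averaged to determine the baseline blood pressure"; Section 8 does not use that value in either BP comparison.

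Section 2.2 lists change in BP first among the secondary endpoints. The proportion below 140/90 is not on that list and appears only in Section 8.

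**The concern.** Starting BP is likely to be among the strongest predictors of final BP, and the trial collects it on everyone who monitors. Subtraction is one particular use of it, best only when the true slope of final on starting BP is 1. With equal variances the slope equals the correlation r, so subtraction over-corrects whenever r is below 1. The control-rate test makes no use of it at all.

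The entry rule adds to this. A subject can qualify on one high screening reading, have a first-week home mean below 140/90, stay there, and be counted as controlled in the final week. Such subjects carry little information about the incentive and dilute the comparison. At stake are wider intervals and less power than the same data allow, in a pilot meant to inform the design of later studies.

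**Working it through.** **The plan's own figure.** There is none to reproduce. Section 4.2 justifies 90 subjects on adherence only; no SD, effect or power is given for either BP comparison. From the documents I take 90 subjects and 1:1 allocation ("Patients will be randomly assigned (1:1) to either receive a social incentive or not"), so 45 per arm. SD = 15 mm Hg, a true difference of 8 mm Hg, and r are assumptions.

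**Change score against regression on the same starting value.** With SD s at both times and correlation r:

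- Var(change) = 2s²(1−r)
- Var(final BP adjusted for starting BP) = s²(1−r²)
- Ratio = (1−r²) / [2(1−r)] = (1+r)/2, below 1 for every r below 1

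The detectable difference at 80% power, two-sided 5%, is (1.96+0.84) × residual SD × √(2/45). With s = 15:

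| r | SD, change | SD, adjusted | Variance ratio | Detectable difference, change → adjusted (mm Hg) | Adjusted power where the change score has 80% |
|---|---|---|---|---|---|
| 0.4 | 16.43 | 13.75 | 0.70 | 9.7 → 8.1 | 91.8% |
| 0.5 | 15.00 | 12.99 | 0.75 | 8.9 → 7.7 | 89.9% |
| 0.6 | 13.42 | 12.00 | 0.80 | 7.9 → 7.1 | 87.9% |
| 0.7 | 11.62 | 10.71 | 0.85 | 6.9 → 6.3 | 86.0% |
| 0.8 | 9.49 | 9.00 | 0.90 | 5.6 → 5.3 | 84.0% |
| 0.9 | 6.71 | 6.54 | 0.95 | 4.0 → 3.9 | 82.0% |

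The ratio and the last column do not depend on the assumed SD.

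**Chance imbalance.** The arm difference in mean starting BP has standard error 15 × √(2/45) = 3.16 mm Hg, so its 95% range is about ±6.2. Given an imbalance of size d, the change-score difference is shifted by (1−r)d and the unadjusted final difference by rd. At r = 0.5 and d = 6.2 each shift is 3.1 mm Hg. Both average to zero over randomisations.

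**Control rate.** Assume SBP only, starting mean 142, common fall 3, effect 8. Then P(final < 140) is Φ(1/15) = 0.527 without the incentive and Φ(9/15) = 0.726 with it. The difference is 0.199, its standard error √[(0.527×0.473 + 0.726×0.274)/45] = 0.0998, and the power of the unadjusted test about Φ(1.99−1.96) ≈ 51%, whatever r is. Simulated logistic regression on arm and starting SBP gives about 52%, 62% and 74% at r = 0.4, 0.6 and 0.8. A separate set of 1,500 runs gave 53%, 60% and 77%, so read these to within about 3 points. Type I error was near 5% for both tests.

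**Already at goal in week 1.** The documents give no data. Assume population mean SBP 140 to 150 and DBP 82, SDs 16 and 10, screening-to-home correlation 0.4 to 0.8, and home SBP 0 to 10 mm Hg below screening. Among subjects meeting the entry rule, the simulated share below 140/90 in week 1 then runs from about 11% to 61%.

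**The case against.** There are good points in favour of the plan as written, and most of them stand.

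- A reader might infer that both analyses ignore starting BP. The change score does not: it subtracts each subject's first-week mean. Only the chi-square comparison leaves it out.
- A reader might infer bias. Allocation is randomised, and both planned tests hold their error rate. Chance imbalance is already covered by that error rate; adjustment narrows the interval but does not repair an invalid test.
- A reader might expect adjustment to stop subjects already at goal from counting as successes. It does not, because the outcome is unchanged. Every subject was above goal at screening, and how many were at goal by week 1 is unknown.
- Each weekly value averages up to 14 readings, which raises r. At r = 0.8 to 0.9 the continuous gain is only 5% to 10% of variance. For the control rate at r = 0.4 the gain is a few points of power at most.
- Week 1 follows randomisation, which Section 7.1 places at enrollment, so an early effect of the incentive could already be in the first-week mean. That is true, but the planned change score removes all of such an effect, and regression removes only about r of it.
- Adherence is primary, the trial is powered on it alone, and the control rate is not a listed endpoint. This limits the importance of the point.

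What remains is that no section adjusts either comparison, and that for any r below 1 regression on the same starting value is the more precise analysis.

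**Conclusion.** The point holds as a matter of efficiency. For change in BP, adjustment cuts the variance of the arm difference to (1+r)/2 of its planned value: 30% less at r = 0.4, 20% less at 0.6, 5% less at 0.9. This rests on equal variances at the two times and on an assumed r. For the control rate, power moves from about 50% to between about 52% and 74% for r from 0.4 to 0.8, under the assumed mean, SD and effect and with SBP alone standing in for the two-part goal. The documents do not support a claim that the planned results would be biased or invalid. Severity is minor: secondary and additional analyses in a pilot, with an easy remedy.

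**What to change.** In Section 8:

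1. Analyse last-week mean SBP and DBP by linear regression on arm plus the same first-week mean the plan already subtracts. Report the adjusted difference with its 95% CI. The rank-sum test on change can stay as a sensitivity analysis if residuals are clearly non-normal.
2. For the zero-change sensitivity analysis, set the final value equal to the starting value. State how a subject with no first-week readings is handled.
3. Because week 1 follows randomisation, add the enrollment clinic BP (Section 7.1) as a further covariate or use it in a sensitivity analysis. Do not simply substitute it. With correlation c between clinic BP and final home BP, it beats the planned change score only if 1−c² < 2(1−r). At c = 0.4 and r = 0.8 it loses: 0.84 against 0.40 of s².
4. Analyse final-week control by logistic regression on arm plus starting SBP and DBP. Keep the raw proportions and their difference beside it, since the adjusted odds ratio is conditional on starting BP and is not the same quantity.
5. Report by arm how many subjects were already below 140/90 in week 1.

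The cost is a few sentences of analysis text. No new data, visits or subjects are needed.
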